13.8.2.2. Secondary Analysis of Primary Endpoint

The treatment effect represented as the recovery rate ratio will be estimated using Cox proportional hazard regression. The Kaplan-Meier estimates of the recovery proportions over time will be provided to graphically present the data. Covariates to be used in the secondary analysis of the primary endpoint will be specified in the Statistical Analysis Plan and will include age and co-existing diseases, such as hypertension and diabetes mellitus.

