13.8.2.1. Primary Analysis of Primary Endpoint

This time to event endpoint will be tested for treatment effect (IC14+SOC vs placebo+SOC) using the stratified log-rank test, as the study will be stratified by groups of study sites and dexamethasone use at baseline.

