13.8.3. Analyses of Secondary and Other Endpoints

Secondary endpoints can be divided into 4 groups: continuous endpoints such as days alive and free of acute respiratory failure through Days 14 and 28, binary endpoints such as participants alive and free of any episode of acute respiratory failure (yes or no), and time to event data such as all-cause mortality and ordinal categorical data such as Ordinal Score at Day 14. These endpoints will be analyzed accordingly based on these categories. Briefly, continuous endpoints will be tested between treatment groups using the Wilcoxon rank sum test. Categorical variables will be compared between groups using Chi-squared test or Fisher exact test based on the number of events. Time to event data will be analyzed using the same methods as for the primary endpoints described above. Ordinal categorical data will be analyzed by the proportional odds logistic model. Covariates for the secondary model-based analyses such as GLM, logistic regression, Cox regression, and proportional odds logistic regression will be described in the Statistical Analysis Plan.

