13.9.2. Interim Analysis of Safety Data

13.9.3. Futility Analysis

13.10. Statistical Hypotheses

The primary hypothesis is that IC14 will be efficacious in treating COVID 19 participants. To test this hypothesis, we will use time to recovery as the primary endpoint. The treatment effect will be presented as the recovery rate ratio. A ratio greater than 1 indicates beneficial effect of IC14. A ratio of 1 corresponds to the null hypothesis that IC14 has no treatment effect compared to placebo.

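### The primary log-rank test uses the randomisation strata, but the Cox rate ratio presented as the treatment effect and the rank-sum, chi-squared and Fisher secondary tests state none

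*Combined protocol and SAP*

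**What the plan says.** Sections 3.4 and 13.1 stratify randomisation by groups of sites and by baseline corticosteroid use. Section 13.8.2.1 carries this into the primary test, "using the stratified log-rank test, as the study will be stratified by groups of study sites and dexamethasone use at baseline".

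The next section turns to estimation: "The treatment effect represented as the recovery rate ratio will be estimated using Cox proportional hazard regression". It mentions no strata. The covariates are left to the Statistical Analysis Plan, and those already named "will include age and co-existing diseases, such as hypertension and diabetes mellitus"; neither randomisation factor is among them. Section 13.10 gives the ratio its role: "The treatment effect will be presented as the recovery rate ratio".

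For secondary endpoints, Section 13.8.3 says that "continuous endpoints will be tested between treatment groups using the Wilcoxon rank sum test" and that "Categorical variables will be compared between groups using Chi-squared test or Fisher exact test based on the number of events". It also says "Time to event data will be analyzed using the same methods as for the primary endpoints described above". Its deferral to the Statistical Analysis Plan is limited to models: "Covariates for the secondary model-based analyses such as GLM, logistic regression, Cox regression, and proportional odds logistic regression will be described".

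Section 13.7 words the site factor differently. It stratifies by study site, for balance within each centre, and Section 8.1 expects about 14 sites.

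**The concern.** The p-value and the headline ratio come from differently specified analyses. A report could show a significant log-rank p-value beside a ratio whose 95% interval includes 1, or the reverse. Section 13.8.2.2 also does not separate a ratio that belongs to the primary test from the covariate-adjusted ratio, so which model gives the headline figure is open. Time-to-event secondary endpoints inherit the stratified log-rank, and with it the same gap in the estimate.

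The unstratified rank-sum, chi-squared and Fisher tests are valid. If the strata are strongly prognostic they are conservative and lose some power. The deferral to the Statistical Analysis Plan covers model covariates and does not reach these tests.

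There are two smaller points:

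- Neither baseline oxygen need nor ordinal category is named for the adjusted model, although both are recorded at baseline (Section 8.3.1, Table 3). The list is open, and Section 13.8.7 suggests that other variables may enter.
- The two wordings of the site factor would give very different numbers of strata.

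**Working it through.** **The plan's own figure.** Inputs from Section 13.11: ratio 1.40, type I error 0.05 (taken as two-sided), 80% power, Weibull shape 0.73, placebo median 6 days. Allocation is 1:1 (Section 13.1) and censoring is at day 28 (Section 13.2.1).

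- Recoveries (Schoenfeld): 4 × (1.960 + 0.842)² / (ln 1.40)² = 31.40 / 0.1132 = 277.3, so 278, as stated.
- 28-day recovery: placebo 1 − 0.5^((28/6)^0.73) = 0.882; IC14 1 − 0.118^1.40 = 0.950, as in Table 7.
- Participants: 278 / 0.916 = 304, against 302 stated.

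The formula has no stratum term, so stratifying the Cox model changes neither figure.

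**Simulation set-up.** 302 participants; permuted blocks of 4 or 6 within strata; placebo median held at 6 days; ratio 1.40 within strata; 28-day censoring; 5000 trials per setting. Assumed, because the documents are silent: 3 site groups × steroid yes/no (six strata), and the stratum effects. Monte Carlo error is about 0.6 points for power and 0.3-0.6 for unstratified or adjusted disagreement.

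**(1) Disagreement on significance with the stratified log-rank, treatment-only Cox**

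| Recovery rates by steroid | Unstratified, 50% on steroid | Unstratified, 80% on steroid | Stratified |
|---|---|---|---|
| equal | 3.8% | 4.1% | 0.1-0.2% |
| 1.5-fold | 5.3% | 5.6% | 0.1-0.2% |
| 2-fold | 8.7% | 7.0% | 0.1-0.2% |

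The 8.7% splits into 6.9% with a significant log-rank beside an interval including 1, and 1.8% the reverse. With recovery times in whole days, the unstratified figures are 4.1, 5.7 and 9.1%, against 1.1, 1.0 and 1.3% stratified.

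At 50% on steroid, Cox power unstratified against stratified is 79.2 v 78.1%, 77.0 v 77.8% and 72.5 v 77.4%. The mean ratio is 1.40, 1.39 and 1.37 unstratified, and 1.40 stratified throughout. That drop is non-collapsibility, not bias. With a true ratio of 1.0 and 2-fold strata, rejection is 3.8% (unstratified Cox), 4.8% (stratified Cox) and 4.9% (log-rank).

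Repeats with separate code and six strata gave unstratified disagreement of 3.4-3.6%, 4.7-6.5% and 8.9-9.6%, against 0.1-0.3% stratified. A variant with 4 site groups, 70% on steroid and stronger assumed effects gave 6 to 20%.

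**(2) Covariate-adjusted Cox** (1.5-fold strata; age and comorbidity prognostic with SD 0.3 on the log-rate scale, correlation 0.3 with severity)

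| Severity hazard ratio per SD | Disagreement, age/comorbidity without strata | Disagreement, strata and severity added | Stratified power, without v with severity |
|---|---|---|---|
| 1.0 | 10.7% | 10.1% | 76.7 v 76.7% |
| 1.35 | 13.4% | 17.1% | 71.1 v 75.9% |
| 1.65 | 15.3% | 22.5% | 64.0 v 75.0% |

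An adjusted ratio can gain precision, but it cannot be the estimate matched to the log-rank.

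**(3) Secondary tests** (assumed placebo failure risks in the two steroid strata, odds ratio 0.42)

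| Risks | Chi-squared v CMH power | Wilcoxon v van Elteren power |
|---|---|---|
| 20/20% | 74.2 v 74.1% | 73.6 v 73.6% |
| 15/30% | 77.1 v 77.7% | 76.5 v 76.9% |
| 10/30% | 71.3 v 72.8% | 70.4 v 71.7% |
| 10/40% | 77.0 v 79.5% | 75.7 v 77.7% |

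Null rejection at 10/40%: chi-squared 4.0%, CMH 5.2%, Wilcoxon 3.8%, van Elteren 5.0%. In the other settings all four lie at 4.7-5.4%.

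**(4) Site or site group.** Individual sites give 14 × 2 = 28 strata, or 302 / 28 ≈ 11 participants each. Cox power then falls from 79.3% unstratified to 71.4% stratified. The log-rank has 71.6%, against about 78% with six strata; repeats gave about 73%.

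**The case against.** **Not stated is not ruled out.** Cox covariates are deferred to the Statistical Analysis Plan, the named list is open, and adjusted models for secondary endpoints are foreseen. This stands as a limit on the claim. It does not reach the rank-sum, chi-squared and Fisher tests, and it does not settle which Cox model gives the headline ratio.

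**Baseline disagreement.** Some 3.8% of trials disagree even when the strata are irrelevant. Prognostic strata add only 1.5 points (1.5-fold) to 4.9 points (2-fold) at 50% on steroid, and none of these strengths is in the documents. That is correct, but stratifying removes the 3.8% as well. Section 13.11 itself shortens the placebo median from 7 to 6 or 5 days partly for corticosteroid use. At shape 0.73 that is a rate shift of (7/6)^0.73 = 1.12 to (7/5)^0.73 = 1.28. This is not a within-trial contrast, but it shows that the factor is thought to bear on recovery.

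**Small secondary gains.** They run from −0.1 to 2.5 points for CMH and from 0 to 2.0 for van Elteren, with the largest under a 10/40% split. This stands; it is the weakest part of the point.

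**Severity adjustment.** It increases disagreement with the log-rank when severity is prognostic, and eligibility narrows the severity range. Both are true. Hence it belongs in a separate, labelled analysis. Oxygen need can still range from room air to just below high-flow under Section 4.2.

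**The 28-strata case is remote.** Section 13.7 is the outlier; Sections 3.4, 13.1 and 13.8.2.1 all refer to groups of sites. Agreed, and it is a wording correction, but the loss if it were implemented is about 5 to 7 points.

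**Conclusion.** The concern holds. The plan stratifies its primary test but not, as written, the ratio it presents as the treatment effect, nor its rank-sum, chi-squared and Fisher secondary tests. Under the assumed six strata, an unstratified treatment-only ratio contradicts the log-rank on significance in about 4 to 9% of trials, which stratifying nearly eliminates. For the secondary tests the gain is at most about 2.5 points of power. There is no type I error inflation, no sample-size error and no change to primary log-rank power. The sizes depend on assumed stratum effects, number of site groups and steroid share, so confidence in them is moderate. The change should be made because it is cheap and the headline estimate would then match the primary test.

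**What to change.** 1. In Section 13.8.2.2, report as the main effect estimate, beside the log-rank p-value, a treatment-only Cox ratio stratified by the same factors.
2. Keep the covariate-adjusted Cox model as a separate, labelled analysis, also stratified. Add baseline oxygen requirement (or ordinal category, if it varies) to age and comorbidity, and state that it need not agree with the log-rank.
3. In Section 13.8.3, use the van Elteren test for continuous and stratified CMH for binary secondary efficacy endpoints, with an exact stratified test if events are few.
4. Name the strata once, as site groups by baseline corticosteroid use, and reconcile Section 13.7.

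The interim futility Cox model in Section 13.9.1 can stay as it is. Stratifying it alone left the stopping probabilities essentially unchanged, and adding severity would require Table 6 to be simulated again.

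Cost: wording in Sections 13.7 and 13.8 and a little analysis work. All variables are already collected, and no participants or visits are added. If nothing is prognostic, Cox power falls by 1.0 to 1.6 points with six strata (largest case 79.5% to 77.9%), a cost the primary log-rank already carries.

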13.8.3. Analyses of Secondary and Other Endpoints

Secondary endpoints can be divided into 4 groups: continuous endpoints such as days alive and free of acute respiratory failure through Days 14 and 28, binary endpoints such as participants alive and free of any episode of acute respiratory failure (yes or no), and time to event data such as all-cause mortality and ordinal categorical data such as Ordinal Score at Day 14. These endpoints will be analyzed accordingly based on these categories. Briefly, continuous endpoints will be tested between treatment groups using the Wilcoxon rank sum test. Categorical variables will be compared between groups using Chi-squared test or Fisher exact test based on the number of events. Time to event data will be analyzed using the same methods as for the primary endpoints described above. Ordinal categorical data will be analyzed by the proportional odds logistic model. Covariates for the secondary model-based analyses such as GLM, logistic regression, Cox regression, and proportional odds logistic regression will be described in the Statistical Analysis Plan.

13.8.4. Analyses of Safety Endpoints

Safety endpoints include continuous endpoints such as change from baseline in liver, renal, hematological, and coagulation function and binary endpoint such as adverse events. The continuous endpoints will be summarized for the treatment groups using mean \pm SD, median and interquartile range and tested using the Wilcoxon rank sum test between groups. The binary adverse event endpoints will be summarized for the treatment groups using count and proportion tested using Chi-squared test or Fisher exact test based on the number of events. The safety data analysis will be conducted at each interim analysis and reported to the DSMB.

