An NIH-sponsored double-blind randomized placebo-controlled phase 2 study of 13 critically ill patients supports the use of IC14 to treat lung injury resulting from increased epithelial and endothelial permeability. In this study, IC14 or placebo were administered to critically ill patients with ARDS at the University of Washington (Seattle, WA). Patients with ARDS were randomized to receive either IC14 4 mg/kg/day x 1 day and 2 mg/kg/day x 3 days (n = 7) or placebo for 4 days (n = 6). Bronchoalveolar lavage (BAL) was performed at baseline and again on Days 2-3 and 5-7 to measure leukocyte counts and differentials, total protein, and pro-inflammatory cytokines and chemokines in the BAL fluid. This trial was stopped early because patients were being enrolled in competing trials; nevertheless, the data showed trends for reductions in total and percentage of neutrophils in lung lavage fluid, as well as plasma IL-6 and IL-8, consistent with an improvement in lung and systemic inflammation (Figure 1 below). Notably, the pre-treatment BAL markers of lung inflammation were higher in the IC14-treated participants, suggesting worse lung inflammation at baseline. No IC14-related safety concerns were noted. Taken together, this trial suggests that administration of IC14 is feasible and safe in critically ill patients with ARDS and may reduce markers of inflammation indicative of breakdown of the endothelial and epithelial permeability barrier.

		Day 1 (baseline)	Day 3	Day 7
Plasma IL-6 pg/ml Median (IQR)	IC14	449.8 (42.4-4867.2)	109.5 (42.4-267.3)	90.2 (4.8-108.9)
	Placebo	180.8 (92.8-371.3)	75.3 (42.4-586.0)	319.1 (121.8-516.4)
BALF IL-6 pg/ml Median (IQR)	IC14	1047.6 (227.9-1396.2)	41.6 (25.6-738.3)	23.8 (4.8-45.2)
	Placebo	79.6 (7.0-979.7)	200.4 (13.3-4147.4)	173.6 (21.1-326.1)

Figure 1. IC14 Pilot Trial in ARDS

A phase 2, randomized double-blind study of IC14 in 180 patients with community-acquired pneumonia did not show a significant decrease in incidence of therapeutic failure, but the treatment was well tolerated with no significant increase in TEAEs, SAEs, or secondary infections (ICOS Abbreviated Clinical Study Report 2004).

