2.2. Secondary Objectives

1. Determine the efficacy of IC14 in reducing the severity of respiratory disease in patients hospitalized with respiratory disease due to SARS-CoV-2.
2. Determine the safety of IC14 in patients hospitalized with respiratory disease due to SARS-CoV-2.

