5.1. Risks of Investigational Product in Clinical Studies

To date, 168 healthy volunteers and patients have received IC14, across a range of clinical studies, LPS challenge (Verbon 2001), community-acquired pneumonia (Axtelle et al. 2003), sepsis (Reinhart et al. 2004;), acute lung injury, and amyotrophic lateral sclerosis. IC14 was generally well tolerated. Adverse events that were at least 5% more common in participants receiving IC14 compared to placebo (regardless of whether they were considered related to IC14 or were due to the underlying disease) are below:

Table 1. Adverse Events Observed with IC14

Side Effect	How often is it likely to occur?	How severe might it be?	How long might it last?
Low platelets (blood clotting cell)	8.3% (2.7% in placebo)	mild-moderate	One week

One SAE occurred (hypotension and rash) in a treated patient with sepsis, which resolved with ranitidine, dimetindine, and prednisolone.

No anti-drug antibodies have been detected in 168 participants treated with IC-14.

In separate randomized placebo-controlled studies of patients with community acquired pneumonia, sepsis or ARDS the number of patients thought to have new bacterial infections after beginning IC14 treatment was balanced across placebo and IC14 groups. In addition, hepatobiliary and renal failure serious adverse events occurred more often with IC14 than placebo (hepatobiliary events 3.8% in IC14 vs. 0% in placebo; renal failure events 5.3% in IC14 vs. 0.9% in placebo).

In studies of IC14 in non-human primates, small numbers of vitreous cells were noted in animals treated with IC14 daily for 14 days that resolved over the following 28 days. These changes were not associated with pathological findings in the eyes and were considered of minor toxicological significance. Eye findings have not been observed in 63 human participants treated with IC14 who had one or more ophthalmologic and/or slit lamp examinations and there were no pathological findings in the eyes of 20 non-human primates that were treated with weekly intravenous doses of either 20 mg/kg/week or 50 mg/kg/week for 26 weeks.

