13.11. Sample Size Calculations

It is assumed that the placebo arm will have a similar recovery experience as shown for the remdesivir arm in Panel C of Figure 2 in the ACTT-1 study (Beigel et al. 2020). The time to recovery can be modeled using the exponential or the Weibull distribution to describe this experience. The exponential distribution assumes constant hazard and the Weibull distribution assumes the hazard decreases with time. The Weibull distribution with shape parameter 0.73 and median time to recovery of 7 days appears to fit the recovery curve better than the exponential for the remdesivir group in ACTT-1. The first column in Table 7 below assumes the Placebo arm in this study will have almost identical recovery experience as the remdesivir arm in ACTT-1. The second and the third column (median time to recovery of 6 and 5 days, respectively) assume improved recovery rate in our Placebo arm (0.882 and 0.913 versus 0.851) when factoring in corticosteroid use and evolving SOC in general. The sample size required for risk ratios ranging from 1.35-1.5, is shown in Table 7. and suggests a sample size of approximately 350 participants will have 80% power to detect a risk ratio of 1.37.

Table 7 shows the sample size needed to have 80% power with type I error rate of 0.05 to detect various RR for differing values of median days to recovery in the SOC+placebo arm. The entries in the cells show the sample size needed along with expected 28-day recovery rates in the placebo vs. IC14 arms.

Table 7. Sample Size Calculations			
	Standard of Care Group: Median Days to Recovery		
Effect (RR)	7	6	5
1.35	392 ^a 0.851 / 0.924 ^b	382 0.882 / 0.944	372 0.913 / 0.963
	312 0.851 / 0.931	302 0.882 / 0.950	296 0.913 / 0.967
1.40	254 0.851 / 0.937	248 0.882 / 0.955	242 0.913 / 0.971
	212 0.851 / 0.943	208 0.882 / 0.959	202 0.913 / 0.974

a. Sample size (n) b. Recovery rate (placebo arm / IC14 arm)

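### Binary safety endpoints get counts, proportions and a significance test but no between-arm estimate or interval, so a non-significant result cannot show whether the excesses in Section 5.1 are excluded

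*Combined protocol and SAP*

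**What the plan says.** Section 2.2 makes safety an objective: "Determine the safety of IC14 in patients hospitalized with respiratory disease due to SARS-CoV-2". Section 13.8.4 sets out the analysis: "The binary adverse event endpoints will be summarized for the treatment groups using count and proportion tested using Chi-squared test or Fisher exact test", with the choice of test resting on how many events there are. Laboratory changes are summarised by mean, SD, "median and interquartile range and tested using the Wilcoxon rank sum test between groups". The same section adds: "The safety data analysis will be conducted at each interim analysis and reported to the DSMB".

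No safety section names a between-arm risk difference, risk ratio, confidence interval, bound, significance level or power. The recovery endpoint, by contrast, has a rate ratio from a Cox model (Section 13.8.2.2). Sample size is set for recovery only: Section 13.11 gives the "sample size needed to have 80% power with type I error rate of 0.05".

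Section 5.1 reports serious events in earlier IC14 studies: "hepatobiliary events 3.8% in IC14 vs. 0% in placebo; renal failure events 5.3% in IC14 vs. 0.9% in placebo". Its Table 1 gives low platelets as 8.3% on IC14 and 2.7% on placebo. Section 12.4.3.1 lists hepatobiliary disorders, acute renal failure and new thrombocytopenia among the adverse events of special interest (AESIs), but no between-arm analysis specific to AESIs is described.

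**The concern.** Three organ signals are already known, so the useful safety question is whether this trial confirms or excludes excesses of that size. A p-value against no difference does not answer it. With few events, a non-significant test is compatible both with no excess and with the whole of the earlier one.

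Without a pre-specified interval, nothing in the planned output separates those two cases. The protocol's own background shows how such a result can be worded. Section 1.3 says of the 180-patient pneumonia study that "the treatment was well tolerated with no significant increase in TEAEs, SAEs, or secondary infections". The same form of summary also goes to the DSMB at its unblinded reviews, where numbers are half or less of the final total.

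**Working it through.** **1. The plan's own figure.** The documents give a power calculation for recovery only. By Schoenfeld's formula, events = 4(z₀.₉₇₅ + z₀.₈₀)² / (ln RR)² = 4(1.960 + 0.842)² / (ln 1.4)² = 4 × 7.849 / 0.1132 = 277.3, so 278, as stated in Section 13.11. With 28-day recovery of 0.882 and 0.950 (Table 7), the mean is 0.916 and 278 / 0.916 = 303.5 participants, against 302 stated. The figure reproduces with a two-sided 0.05 level. There is no corresponding safety figure to reproduce.

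**2. Inputs for the safety tests.**
- Rates, IC14 versus placebo (Section 5.1): renal failure 5.3% v 0.9%; hepatobiliary 3.8% v 0%; low platelets 8.3% v 2.7%.
- Sizes: about 300 at 1:1 is 150 per arm; the cap of 350 is 175 per arm; the 150-completer review is taken as 75 per arm.
- Assumptions: the earlier rates carry over; tests are two-sided at 0.05 (no level is given for safety); data are complete; chi-squared is uncorrected. Section 13.8.4 lets the number of events decide between the two tests without giving a cut-off, so both are shown.

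**3. Probability of a non-significant result.** With a events on IC14 and b on placebo,

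P(non-significant) = 1 − Σₐ Σ_b Bin(a; n, p₁) · Bin(b; n, p₀) · 1{p-value(a, b) ≤ 0.05},

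summed over all tables.

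| Per arm | Event | Fisher | Chi-squared |
|---|---|---|---|
| 75 | Renal | 88% | 67% |
| 75 | Hepatobiliary | 93% | 68% |
| 75 | Platelets | 81% | 68% |
| 150 | Renal | 52% | 38% |
| 150 | Hepatobiliary | 49% | 17.5% |
| 150 | Platelets | 53% | 42% |
| 175 | Renal | 43% | 30% |
| 175 | Hepatobiliary | 34% | 10% |
| 175 | Platelets | 44% | 35% |

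The hepatobiliary row can be checked by hand, because at a placebo rate of 0% only a varies. At 150 per arm, Fisher gives p = 0.060 for 5 v 0 and 0.030 for 6 v 0, so at least 6 events are needed. With X ~ Bin(150, 0.038), P(X ≤ 5) = 0.493. Chi-squared gives z = 1.74 for 3 v 0 and 2.01 for 4 v 0, so 4 events suffice, and P(X ≤ 3) = 0.175. The choice of test alone moves the result from 49% to 17.5%.

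**4. What an interval adds.** Take 6/150 v 1/150.
- Fisher p = 0.12. Chi-squared: pooled rate 7/300 = 0.02333; (0.03333)² / (0.02333 × 0.97667 × 2/150) = 3.66, p = 0.056. Neither is significant.
- Wilson limits: 4.00% (1.85 to 8.45) and 0.67% (0.12 to 3.68).
- Newcombe interval for the difference of 3.33 points: lower = 3.33 − √[(4.00 − 1.85)² + (3.68 − 0.67)²] = 3.33 − 3.70 = −0.4; upper = 3.33 + √[(8.45 − 4.00)² + (0.67 − 0.12)²] = 3.33 + 4.48 = +7.8.

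The interval covers zero and also the earlier renal excess, 5.3 − 0.9 = +4.4 points. The p-value alone does not show that.

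**The case against.** Several points on the other side stand.

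- A reader might infer that safety is judged only by p-values. Section 13.8.4 does not support that. Counts and proportions are reported per arm, so a crude difference is one subtraction away. Liver, renal and platelet laboratory values are compared by Wilcoxon test; at 150 per arm with complete data its power for a 0.5-SD shift is about 99%. Section 13.9.1 has the DSMB weigh imbalances with no p-value criterion.
- A reader might infer that the missing interval causes the low power. It does not. The probabilities above come from sample size, event rates and test choice, and would be the same with intervals added.
- A reader might infer that the plan equates non-significance with safety. No rule says so. The wording in Section 1.3 is background about another trial, while Section 5.1 discloses the excesses with no significance filter and Section 12.4.3.1 makes them AESIs, with a monthly aggregate review (Section 12.5.1.1).
- A reader might infer that a null result is nearly certain at the 150-completer review. With chi-squared it is 67–68%.
- The earlier rates come from other populations and are given without denominators. This trial excludes eGFR below 30, AST or ALT above 5 times the upper limit of normal, and platelets at or below 50,000 (Section 4.3).
- DSMB reports follow the SAP and the DSMB charter (Section 12.7.3.1). The text reviewed contains neither as a separate document, so intervals may be specified there.

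The last point does not close the gap. Sections 13.8.2.2, 13.8.3, 13.8.6 and 13.8.7 defer detail to the SAP; Section 13.8.4 does not.

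**Conclusion.** The concern holds in this form: for binary safety endpoints, a chi-squared or Fisher test is the only stated between-arm inference, and no effect estimate or interval is pre-specified. This bears on what the trial can conclude about its own safety objective, since a null test would be a common result even if the Section 5.1 excesses were real. At 150 per arm, the probability for each test is about 49–53% with Fisher or 17.5–42% with chi-squared.

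These are chances for each test separately, not a share of harms missed. They depend on the earlier rates applying here, on a two-sided 0.05 level and on which test is used, so no single figure should be quoted. The need for an interval does not depend on those assumptions.

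**What to change.** In Section 13.8.4, for AEs, SAEs and each AESI in Section 12.4.3.1:

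- Report the risk difference, IC14 minus placebo, with a two-sided 95% CI. Name the method in advance (Newcombe or Miettinen-Nurminen), because interval and test can disagree with sparse counts: 7/150 v 1/150 gives +4.0 points (Newcombe 0.2 to 8.7) with Fisher p = 0.067. A difference also remains defined when placebo has no events, as in the earlier hepatobiliary data.
- Keep the chi-squared or Fisher p-value as descriptive.
- State that a non-significant test is not evidence of safety.
- Put the same intervals in the final analysis and in the unblinded DSMB reports at 75 and 150 completers.

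The cost is a paragraph of text and one extra column in the safety tables, with no new data, visits or participants. The safety statement will look less certain than a p-value makes it appear. No safety power statement is needed in Section 13.11, since it would rest on rates from other populations.
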